The Data and Safety Monitoring Committee (DSMC) of the Winship Cancer Institute will provide oversight for the conduct of this study. The DSMC functions independently within Winship Cancer Institute to conduct internal monitoring functions to ensure that research being conducted by Winship Cancer Institute Investigators produces high-quality scientific data in a manner consistent with good clinical practice (GCP) and appropriate regulations that govern clinical research. Depending on the risk level of the protocol, the DSMC review may occur every 6 months or annually. For studies deemed High Risk, initial study monitoring will occur within 6 months from the date of the first subject accrued, with 2 of the first 5 subjects being reviewed. For studies deemed Moderate Risk, initial study monitoring will occur within 1 year from the date of the first subject accrued, with 2 of the first 5 subjects being reviewed. Subsequent monitoring will occur in routine intervals per the [Winship Data and Safety Monitoring Plan \(DSMP\)](#).

The DSMC will review pertinent aspects of the study to assess subject safety, compliance with the protocol, data collection, and risk-benefit ratio. Specifically, the Winship Cancer Institute Internal Monitors assigned to the DSMC may verify informed consent, eligibility, data entry, accuracy and availability of source documents, AEs/SAEs, and essential regulatory documents. Following the monitoring review, monitors will provide a preliminary report of monitoring findings to the PI and other pertinent individuals involved in the conduct of the study. The PI is required to address and respond to all the deficiencies noted in the preliminary report. Prior to the completion of the final summary report, monitors will discuss the preliminary report responses with the PI and other team members (when appropriate). A final monitoring summary report will then be prepared by the monitor. Final DSMC review will include the final monitoring summary report with corresponding PI response, submitted CAPA (when applicable), PI Summary statement, and available aggregate toxicity and safety data.

The DSMC will render a recommendation and rating based on the overall trial conduct. The PI is responsible for ensuring that instances of egregious data insufficiencies are reported to the IRB. Continuing Review submissions will include the DSMC recommendation letter. Should any revisions be made to the protocol-specific monitoring plan after initial DSMC approval, the PI will be responsible for notifying the DSMC of such changes. The Committee reserves the right to conduct additional audits if necessary.

The PI or designee must provide the DSMC a report outlining the overall enrollment and path to decision for the escalation dose(s) selected.

Additional points in regards to the DSMP specifically for this study:

- After the first subject has enrolled, monthly research meeting will be held by the PI along with selected members of the study team to review toxicity and efficacy data as they are acquired.
- AEs (including SAEs) will be recorded based on planned assessment time points by the CRC and assessed by the PI/sub-investigators according to SOP. These will then be reviewed on an ongoing basis at the monthly research meeting with reports to the DSMC at appropriate times (e.g. to initiate next dose level).
- Oversight of the study team will be carried out at neuro-oncology working group meeting and will include random checks of CRFs/charts.
- Study team will be trained on study procedures at a study initiation meeting prior to study opening. Changes to the study (e.g. Study Amendments) will be communicated to the entire study team by e-mail with documentation that team members acknowledgement their understanding of the changes.

17. Provisions to Protect the Privacy Interests of Participants

Participants will be assured of their voluntary participation in the study, their choice to answer or not answer any question, and the protocol for maintaining confidentiality.

Participant confidentiality is strictly held in trust by the participating investigators, their staff, and the sponsor(s) and their agents. This confidentiality is extended to cover testing of biological samples and genetic tests in addition to the clinical information relating to participants. Therefore, the study protocol, documentation, data, and all other information generated will be held in strict confidence. No information concerning the study or the data will be released to any unauthorized third party without prior written approval of the sponsor.

The study monitor, other authorized representatives of the sponsor, representatives of the IRB or pharmaceutical company supplying study product may inspect all documents and records required to be maintained by the investigator, including but not limited to, medical records (office, clinic, or hospital) and pharmacy records for the participants in this study. The clinical study site will permit access to such records.

The study participant's contact information will be securely stored at each clinical site for internal use during the study. At the end of the study, all records will continue to be kept in a secure location for as long a period as dictated by local IRB and Institutional regulations.

Study participant research data, which is for purposes of statistical analysis and scientific reporting, will be transmitted to and stored. This will not include the participant's contact or identifying information. Rather, individual participants and their research data will be identified by a unique study identification number. The study data entry and study management systems used by clinical sites and research staff will be secured and password protected. At the end of the study, all study databases will be de-identified and archived.

18. Economic Burden to Participants

The study supporter (IBSA) will be providing the study drug for no charge on this study but will not pay for other items and services the subject may receive in this study. Funds associated with this study will be available to cover the cost of research only studies (e.g. the PK and serum biomarker assessments). Subjects will have to pay for the items or services for which the study supporter or the study itself does not pay. The study supporter and the study itself will not pay for regular medical care. If subjects have insurance, Emory will submit claims to the insurance for items and services that are not covered by the study supporter or the study itself. Emory will send in only those claims for items and services that it reasonably believes the insurance will pay and that will not be paid by the study supporter or the study itself. The actual amount that participants have to pay depends on whether or not they have health insurance and whether or not that insurance will pay for any research study costs. Generally, insurance companies will not pay for items and services that are required just for a research study. Some insurance companies will not pay for regular medical treatment or treatment for complications if in a study. If subject do not have insurance, Emory will review that particular case as part of its program for low-income patient care. The standard policies of that program will apply. The program will figure out if subjects have to pay any costs for taking part in the study and what those costs will be.

19. Consent Process

The initial informed consent discussion will occur in Winship Cancer Institute or the Emory Clinic.

At Winship Cancer Institute, the informed consent is an ongoing, interactive process rather than a one-time information session. The consent form document is designed to begin the informed consent process, which provides the patient with ongoing explanations that will help them make educational decisions about whether to begin or continue participating in the trial. The research team knows that a written document alone may not ensure that the patient fully understands what participation means. Therefore, the research team will discuss with the patient the trial's purpose, procedures, risks and potential benefits, and their rights as a participant. The team will continue to update the patient on any new information that may affect their situation.

Consent will be obtained prior to any research-driven procedures. The investigator will assess the patient's capacity during his/her encounters with him or her. The investigator will give the person providing consent adequate opportunity to read the consent document before it is signed and dated.

It will be explained to prospective participants that the study involves research, the purpose of the research, the expected duration of participation, as well as the approximate number of participants to be enrolled. The study procedures, and identification of research procedures v. non-research will also be thoroughly discussed. It will be explained to participants that participation is voluntary and that the subject may discontinue at any time.

Refusal to participate or withdraw will not involve a penalty or loss of benefits to which the participant is otherwise entitled. Refusal will in no way affect the participant's future care. The participant will also be told of the possible consequences of the decision to withdraw from the research, and procedures for orderly termination of participation.

Any significant new findings developed during the course of the research that may affect the participant's willingness to continue to participate will be provided. Also explained will be anticipated circumstances under which the subject's participation may be terminated by the investigator without the participant's consent.

Prospective participants will be provided with a description of any reasonably foreseeable risks or discomforts as well as a description of any benefits to the participant or to others that might be reasons expected from the research. Alternative procedures or courses of treatment will also be thoroughly discussed.

Prospective participants will also be given detailed information describing the extent to which confidentiality of records identifying the participant will be maintained and what records may be examined by the research staff, IRBs, sponsor, their representatives, and possibly the FDA or OHRP.

Also communicated to the participant will be an explanation that emergency medical care will be arranged for a study-related illness or injury, and an explanation of whether funds are set aside to pay for this care and/or compensation, and if so by whom (e.g., sponsor, subject, insurer). The participant is told the source of the study's funding.

All participants will be told of any additional costs that may result from participation in the research.

Consent will be done in person or remotely through secured email, phone or by electronic consenting using one of the methods that is Emory LITS approved (e.g. DocuSign). We will follow Emory's guidance on use of electronic informed consent.

Non-English-Speaking Participants

A certified translator/interpreter will be present during the consenting process and all questions and concerns will be answered by the treating physician.

A Short Form in that specific language will be used. A certified translator/interpreter will be present during the consenting process and this will be documented. We will use what's available on Emory IRB website. For

the languages that are not available, we will have the short form translated to that language and submit the IRB for review and approval prior to use. Process to Document Consent in Writing: Winship SOP 2.1: "Obtaining Informed consent for Interventional clinical trial" will be followed.

Participants who are not yet adults (infants, children, teenagers)

N/A

Cognitively Impaired Adults

N/A

Adults Unable to Consent

A legally authorized representative may take part in the informed consent discussion sign the consent form on behalf of the patient. We will follow Emory IRB P&P in regards to use of LAR.

Waiver or Alteration of Consent Process (consent will not be obtained, required information will not be disclosed, or the research involves deception)

N/A

20. Setting

The research will be conducted at the Winship Cancer Institute of Emory University.

Potential participants will be identified in the clinics for neuro-oncology, neurosurgery, radiation oncology or multidisciplinary brain tumor care as well as at the weekly Adult Brain Tumor Conference at Emory University.

21. Resources Available

Emory University was founded in 1836 and is a national center for teaching, research, and service. Emory University has been named as one of the nation's top 25 universities for more than a decade by the U.S. News and World Report. Emory University research partners include the Georgia Institute of Technology, the University of Georgia, Morehouse School of Medicine, the US Centers for Disease Control and Prevention, Children's Healthcare of Atlanta, and the Georgia Clinical and Translational Science Alliance (GACTSA). Emory University researchers received \$734 million from external funding agencies in fiscal year 2018, including approximately \$441 million in funding from federal agencies, \$359 million of this from the National Institutes of Health (NIH).

Winship Cancer Institute (Winship) is Georgia's first and only National Cancer Institute (NCI)-designated Comprehensive Cancer Center (P30CA138292) and is dedicated to the integration of innovative clinical and basic science research with outstanding patient care for the prevention, treatment and control of cancer. First designated in 2009, Winship's NCI designation was renewed in 2012 and 2016, achieving an "outstanding" rating. Winship earned the prestigious Comprehensive Cancer Center designation from the

NCI in 2016, after demonstrating that its outstanding programs are reducing the cancer burden on the state of Georgia through research conducted in its laboratories, its clinical trial program, and its population-based science. The institutional support for Winship was rated as 'exceptional' by the review panel.

The **Winship Clinic Building C** houses the primary offices and clinical space for cancer services including the medical oncology, hematology, and surgical oncology clinics, the radiation oncology program, and the Winship Ambulatory Infusion Center. In summer 2017, Emory Healthcare completed the expansion of **Emory University Hospital Tower** on Clifton Road. This nine-floor facility adds 144 inpatient beds to the hospital, of which more than 80% are dedicated to cancer care. The hospital expansion also accommodates cancer patient-specific intensive care units, an expanded BMT Unit with peri-transplant clinics to facilitate continuity of care, and a 24-hour cancer urgent care center, which serves as both a triage facility and short stay treatment center for patients with cancer-related medical concerns.

22. References

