1.3 Schedule of Assessments

Tests and procedures	Pre-reg	≤14 days prior to start of therapy	Initial 4 weeks of progesterone therapy				Second 4 weeks of progesterone therapy	Subsequent maintenance progesterone therapy
			d1	d8	d15	d22	d29	Beginning of every 4 week interval to study end (up to 24 wks of therapy) ¹⁰
Informed consent	X							
Path diagnosis	X							
H&P, KPS		X ⁴			X ⁵		X ⁵	X ⁶
Height (only initially), Weight		X			X ⁵		X ⁵	X ⁶
Neuro assessment		X			X ⁵		X ⁵	X ⁶
Adverse event assessment			X	X ⁵	X ⁵	X ⁵	X ⁵	X ⁶
Medical History	X							
Concomitant medication	X	X	X	X ⁵	X ⁵	X ⁵	X ⁵	X ⁶
Initial Consult	X ³							
CBC w/diff		X					X ⁵	X ⁶
CMP ¹		X					X ⁵	X ⁶
Exploratory serum biomarkers		X					X ⁵	
Pharmacokinetic assessment			X ⁸	X ⁸				
MRI w/ & w/o contrast ²		X					X ⁵	X ⁷
Steroid/anti-Sz med documentation		X	X	X ⁵	X ⁵	X ⁵	X ⁵	X ⁶
QOL assessments		X					X ⁵	X ⁹
Pregnancy test		X ¹¹						
Drug diary documentation			X ¹²		X ¹²		X ¹²	X ¹²

Note – AE assessments, concomitant medications and steroid/anti-Sz med documentation at d8 and d22 may be done by telephone, if the patient does not otherwise need to be seen in clinic.

¹ Comprehensive Metabolic Panel (CMP) - Sodium, potassium, bicarbonate, chloride, BUN, creatinine, calcium, glucose, total bilirubin, SGOT (AST), SGPT (ALT), alkaline phosphatase, albumin, total protein (Standard care). The frequency of CMP will be up to the treating physician's discretion.

² Standard diagnostic brain MRI w/ & w/o contrast.

³ Initial consultation by either neuro-oncology or radiation oncology can be completed ≤ 21 days before initiation of therapy.

⁴ May be satisfied by H&P at initial consultation if within 14 days of starting therapy.

⁵ May be assessed ± 3 days.

⁶ May be assessed ± 7 days. Final followup (including AE assessment) will be at 28 days after last drug dose.

⁷ To be assessed after 8 weeks of therapy ± 1 week and then every 8 weeks ± 2 weeks, thereafter. Other MRIs can be done at discretion of treating physician, if needed.

- ⁸ To be performed on day 1 (0, 30 minutes, 1, 2, 4, 6, 8 hrs from drug injection) as well as at day 8 prior to drug injections on those days only in patients getting PK evaluations. (May alternatively be done on any day after the 1st week during the initial 4 weeks with no need for day 8 trough draw if done later)

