1-2 of 6 with DLT → **expand Level 1 to 20 patients**
3-4 of 6 with DLT → **expand Level 0 to 20 patients**
2-3 of 3 with DLT → **expand Level 0 to 20 patients**

During the dose finding phase of the study, a treatment will be considered safe/tolerable if no DLT defined as \geq grade 3 toxicity during the first 4 weeks drug therapy not clearly due to the underlying disease or extraneous causes with exceptions as noted in **Section 5.3**. After treatment initiation of up to 6 patients at a dose level and continuation for a minimum of 4 weeks with AE assessment, enrollment to the next (higher or lower) dose level as determined by the rules will only start after data is presented to the Winship Data Safety Monitoring Committee (DSMC) and final approval is obtained for starting the next dose level.

Dose escalations will be reviewed by the Winship Data Safety Monitoring Committee (DSMC) (per Winship SOP 7.9 Dose Escalation Determinations for Sponsor-Investigator or Investigator Initiated Studies). The PI or designee will provide an update on all relevant safety data of patients entered to a dose level to the DSMC when dose escalation is planned. Upon obtaining approval from the DSMC, dose escalation can proceed.

Dose Expansion Phase (Part 2):

The purpose of cohort expansion is to gather additional safety and tolerability information, and evaluate the efficacy of aqueous natural progesterone for injection at the dose determined by the Dose Finding Phase of the study.

The PI or designee must provide the DSMC a report outlining the overall enrollment and path to decision for the escalation dose(s) selected.

Continuous evaluation of toxicity events in the cohort expansion will be performed throughout enrollment in the expansion cohort. If, at any time, the aggregate rate of treatment-related toxicities meeting DLT criteria exceeds 33% across all subjects treated in the expansion cohort, the findings will be discussed and further enrollment may be interrupted. Depending on the nature and grade of the toxicity and after assessing the risk:benefit ratio, a new dose(s) for all cohorts may be initiated at a previously tested lower dose level, or at a dose level intermediate to previously tested lower dose levels.

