5.3 Definition of Dose-Limiting Toxicity

The safety of this approach will be confirmed by assessing toxicity potentially attributable to the daily progesterone treatment. National Cancer Institute Common Terminology Criteria for Adverse events version 5.0 (NCI CTCAE v. 5.0) will be used for all grading. A dose limiting toxicity (DLT) is defined as an adverse event or abnormal laboratory value assessed as grade 3 or greater that is not clearly due to the underlying disease or extraneous causes with the following exceptions:

- Grade 3 nausea/vomiting or diarrhea for less than 72 hours with adequate antiemetic and other supportive care.
- Grade 3 fatigue for greater than 1 week.
- Grade 3 or higher electrolyte abnormality that lasts up to 72 hours, is not clinically complicated, and resolves spontaneously or responds to conventional medical interventions.
- Grade 3 or higher amylase or lipase that is not associated with symptoms or clinical manifestations of pancreatitis.
- Grade 3 neutropenia.
- Grade 3 thrombocytopenia without clinically significant bleeding.

For the Dose Finding Phase of the study, the dose will be deemed tolerable if no DLTs occurs within the first 4 weeks of progesterone treatment. Prior to enrolling patients into a higher dose level, CTCAE grade ≥ 2 adverse events will be reviewed for all patients at the current dose level.

Management and dose modifications associated with adverse events are outlined in **Section 5.4**.

Dose escalation will proceed to different dose levels according to the scheme presented earlier (**Section 5.2**).

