15.1 Statistical consideration section: Biostatistician

This is a single arm, Phase 1 study, designed to evaluate the pharmacokinetics, safety/tolerability and efficacy of subcutaneously administer natural progesterone in subjects with recurrent glioblastoma (GBM). The study consists of two parts: Part 1) Dose finding phase; Part 2) Dose expansion phase.

Statistical design and sample size:

Dose finding phase (Part 1):

The dose finding phase will proceed using a standard 3+3 approach in order to identify the maximum tolerated dose (MTD). The study will start at Dose Level 0 with dose moving according to protocol criteria

Protocol Title: Pilot study of progesterone for recurrent GBM

(Section 5.2). For the 3+3 dose finding phase, a dose limiting toxicity (DLT) will be defined as a grade 3 or

greater toxicity that is not clearly due to the underlying disease or extraneous causes that develops in the first 28 days of starting progesterone (exceptions as noted in **Section 5.3**). Dose levels are shown on the following table:

Dose Level	Daily subcutaneous dose (mg)
-1	25
0	50
1	75

After treatment initiation of up to 6 patients at a dose level and continuation for a minimum of 4 weeks with AE assessment, enrollment to the next (higher or lower) dose level as determined by the rules will only start after data is presented to the Winship Data Safety Monitoring Committee (DSMC) and final approval is obtained for starting the next dose level. The sample size in the dose finding phase will range from 6-12.

Dose expansion phase (Part 2):

A total of 20 patients will be enrolled at the MTD (including those in the Dose finding phase at this dose level) in the dose expansion phase unless futility criteria for the expansion cohort is met. The MTD from the dose finding phase (25 mg, 50 mg, or 75 mg) administered subcutaneously 1x/day will be given in this expansion cohort until 20 patients have initiated the dose determined from the dose finding phase. The objective of the dose expansion phase is to provide a preliminary efficacy assessment, and thus no further justification for this sample size is required.

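### Grade 3+ laboratory DLTs count only in the first 28 days, but the first required on-treatment labs are at d29 ± 3, and the plan does not say whether a toxicity first found there counts

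*Combined protocol and SAP*

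**What the plan says.** Three sections set the DLT window, and they agree on its length. Section 5.2 refers to "toxicity during the first 4 weeks drug therapy". Section 5.3 judges a dose tolerable "if no DLTs occurs within the first 4 weeks of progesterone treatment". Section 15.1 limits DLTs to toxicity "that develops in the first 28 days of starting progesterone".

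Section 5.3 expressly includes laboratory findings. A DLT is an "adverse event or abnormal laboratory value assessed as grade 3 or greater", unless clearly due to the disease or another cause, with a list of exceptions.

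The Schedule of Assessments (Section 1.3) requires CBC and CMP at screening, at d29, and every 4 weeks after that. The d1, d8, d15 and d22 cells are empty for both tests. Footnote 5, attached to the d29 entries, reads "May be assessed ± 3 days". The table places d29 under the second 4 weeks of therapy, not the initial 4 weeks. Section 5.6 lists CBC and CMP for the treatment phase without giving days.

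No section says whether a laboratory toxicity first found at the d29 visit belongs to the DLT window.

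**The concern.** The 3+3 rules in Sections 1.2 and 5.2 turn on single events. At Level 0, no DLT in three patients leads to Level 1, one leads to three more patients, and two lead to a lower dose. Whether one laboratory value counts can change the dose decision and the MTD.

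Hepatic and renal values can be abnormal without symptoms, so the weekly adverse event checks (by telephone if need be at d8 and d22) may not reveal them. The first scheduled chance to see them straddles the end of the window. Two patients with the same toxicity could be classified differently because one was drawn on d27 and the other on d30.

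The condition for moving to another dose level does not close the gap. Sections 5.2 and 15.1 ask for at least 4 weeks of treatment with adverse event assessment and for committee approval. They do not require the d29 laboratory results to be in hand.

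**Working it through.** **1. Window length.** 4 weeks × 7 = 28 days, so Sections 5.2, 5.3 and 15.1 are consistent with one another. The mismatch is between them and the laboratory schedule.

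**2. Draw days against the window.** The inputs are the d29 visit and its ± 3-day allowance (Section 1.3), with the first dose on d1. The permitted days are 26, 27, 28, 29, 30, 31 and 32.

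- Study days 1 to 28: d26–d28 are inside (3 of 7) and d29–d32 outside (4 of 7), including the nominal day.
- 28 elapsed days after d1: d26–d29 are inside (4 of 7) and d30–d32 outside (3 of 7).

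**3. Effect on escalation (illustration).** Under the Level 0 rule in Section 5.2, the dose moves up after 0 of 3, or after 1 of 3 followed by 0 of the next 3. With counted DLT probability q per patient and independent patients:

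P(escalate) = (1 − q)³ + 3q(1 − q)² × (1 − q)³

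Let p be the true rate of DLTs visible only at the d29 ± 3 draw, and m the share not counted, so q = p(1 − m). The values of p are assumptions; the documents give none. Taking m as 3/7 or 4/7 assumes that draws are uniform over the seven days and that values found after the window are not counted.

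| True rate p | All count (m = 0) | m = 3/7 | m = 4/7 |
|---|---|---|---|
| 20% | q = 0.200: 71% | q = 0.114: 88% | q = 0.086: 93% |
| 33% | q = 0.330: 43% | q = 0.189: 73% | q = 0.141: 83% |
| 50% | q = 0.500: 17% | q = 0.286: 52% | q = 0.214: 68% |

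Worked cell, p = 33% and m = 0: 0.67³ + 3 × 0.33 × 0.67⁵ = 0.301 + 0.134 = 0.434.

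If every such draw fell outside the window and none counted, q = 0 and P(escalate) = 100%. That is only an upper bound.

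**The case against.** The case on the other side has real substance.

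- **The window may include d29.** Day 29 is exactly 28 days after d1. Sections 5.6 and 5.7 treat the serum biomarker sample from the same visit as a 4-week sample, and weekly checks after d1 fall on d8, d15, d22 and d29. This reading is plausible, but d30–d32 still fall outside, and the schedule's own column heading puts d29 in the second 4 weeks.
- **Onset is not detection.** Section 15.1 speaks of when a toxicity develops, so a value found on d30 may be judged to have begun by day 28. That is correct, but no attribution rule is given, so each case would be decided after the result is known.
- **Other labs are possible.** CMP frequency is at the physician's discretion (Section 1.3, footnote 1), and Section 5.6 allows repeat testing on clinical grounds. Neither is required, and a silent toxicity may not prompt a test.
- **Several laboratory events are exempt.** Section 5.3 excludes grade 3 neutropenia, grade 3 thrombocytopenia without significant bleeding, short uncomplicated electrolyte abnormalities and asymptomatic amylase or lipase rises. This narrows the haematologic and electrolyte part of the point. Hepatic and renal values have no such exemption.
- **Escalation is not automatic.** The DSMC must approve it after a safety update (Sections 5.2 and 15.1), and grade 2 or higher events are reviewed before a higher level opens (Section 5.3). A known d29 finding could reach the decision-makers, but neither review defines the DLT count that the 3+3 rule uses.

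A reader might infer that the whole class of laboratory DLTs becomes visible only after the window closes. The documents do not support that: draws on d26–d28 are inside on any reading, and unscheduled labs are allowed. A reader might also infer that escalation becomes certain. That needs every DLT to be laboratory-only, every draw to fall late, and every late value to be judged as having begun after day 28. The adverse reaction table in Section 13 lists no hepatic, renal, electrolyte or haematologic reaction. It is a summary from treated women, but it gives no support for high laboratory-only rates.

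**Conclusion.** The point holds as a mismatch between the DLT window and the laboratory schedule, with no rule to resolve it. Followed literally, the plan can leave a grade 3 or higher laboratory toxicity out of the 3+3 count because of the day on which blood was drawn. The exposed part of the visit window is 4 of 7 days, or 3 of 7 under elapsed days.

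The day counts follow directly from the text. The escalation probabilities are conditional on the assumptions stated with them and do not forecast this drug's behaviour. Committee and grade 2+ review lower the practical risk. The matter should still be settled in the text, because the count determines the MTD and the repair is small.

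**What to change.** Reconcile Sections 5.2, 5.3 and 15.1 with the Schedule of Assessments so that all four say the same thing:

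- The full 28 days remain the minimum DLT window for every patient. The window should not simply end at the d29 visit: that visit may take place as early as d26, and toxicities on d27 and d28 that count today would then be lost. A 28-day minimum also fits the 28-day replacement threshold in Section 12.
- Results of the CBC and CMP drawn at the d29 ± 3 visit enter the DLT count, subject to the existing Section 5.3 exceptions and attribution wording.
- Those results are available before the cohort decision goes to the DSMC.

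The cost is a sentence or so in each section. No extra blood draw is needed. Cohort review may wait a few days at most, and slightly more DLTs may be counted.
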